### **Title of Study:**

A Phase IV, Open-Label, Multi-center study to evaluate the Safety and the 1-year persistence of antibody response among children who received 4 doses of the Novartis MenACWY Conjugate Vaccine at 2, 4, 6 and 12 months of age in South Korea.

Study Period: The duration of study	Clinical Phase: Phase IV
participation for each subject is	
approximately 22 months.	

# **Background and Rationale:**

The purpose/aim of this study is to evaluate the persistence of the antibody response in children approximately 24 months of age who receive 4 doses of Menveo® at 2, 4, 6,12 months of age.

Neisseria meningitidis is a leading cause of bacterial meningitis and sepsis worldwide, (Rouphael and Stephens 2012, Al-Tawfiq et al 2010, Hill et al 2010, Deasy and Read 2011) capable of causing outbreaks and epidemics of invasive disease. Meningococcal disease causes high rates of morbidity and mortality even among patients who receive early antibiotic treatment. Based on antigenic differences in their capsular polysaccharide, 13 serogroups of *N. meningitidis* have been identified. Virtually all disease-associated isolates are encapsulated, with serogroups A, B, C, Wand Y being responsible for the large majority of invasive meningococcal infections worldwide.

Novartis developed a quadrivalent meningococcal vaccine against serogroups A, C, W and Y (MenACWY-CRM, Menveo®) which is licensed in more than 60 countries. Recently this vaccine was approved for use in infants as young as 2 months of age in the US, Argentina, South Korea and other countries. MenACWY-CRM is given to infants as a 4-dose series at 2, 4, 6, and 12 months of age; children 7 to 23 months of age should receive a 2-dose series, with the second dose administered in the second year of life.

Previous studies have shown that MenACWY-CRM is immunogenic and well tolerated

Doc Number: 68901057

Name of Sponsor:	Protocol number:	Generic name of study vaccine(s):
Novartis Pharma Services AG	V59_75	MenACWY-CRM (Menveo®) is a Meningococcal (Groups A, C, Y and W-135), Oligosaccharide Diphtheria CRM 197 Conjugate Vaccine.

when administered at 2, 4, 6 and 12-13 months of age, or when administered to toddlers as 1 or 2 doses in the second year of life. Limited data are available about long-term persistence of bactericidal antibodies following a 4-dose vaccination series in infants.

Novartis MenACWY (Menveo® has been approved for use in people 2 months through 55 years of age in the United State and in people 2 years up to 55 in Europe and other countries, including the Republic of South Korea. In South Korea, the indication was extended in May 2014 to infants 2 months of age up to 55, however, the Ministry of Food and Drug Safety (MFDS) of the Republic of South Korea have requested data on immunogenicity persistence in the Korean children who received 4 doses of Menveo® at 2, 4, 6, and 12 months of age.

### **Study Objectives:**

# **Primary Objective(s):**

- 1. To evaluate the persistence of the antibody response against *N. meningitidis* serogroups A, C, W and Y at approximately 1 year after completion of a 4-dose infant vaccination series (2, 4, 6 and 12 months of age) of MenACWY vaccine as measured by hSBA titers ≥8.
- 2. To evaluate the persistence of the antibody response against *N. meningitidis* serogroups A, C, W and Y at approximately 1 year after completion of a 4-dose infant vaccination series (2, 4, 6 and 12 months of age) of MenACWY vaccine as measured by rSBA titers ≥8 and ≥128.

## **Secondary Objective(s):**

- 1. To describe hSBA titers ≥8 and hSBA GMTs against *N. meningitidis* serogroups A, C, W and Y 1 month after a full vaccination series at 2,4,6 and 12 months of age.
- 2. To describe rSBA titers ≥8 and ≥128 and rSBA GMTs against *N. meningitidis* serogroups A, C, W and Y 1 month after a full vaccination series at 2,4,6 and 12 months of age.
- 3. To evaluate the persistence of the antibody response against *N. meningitidis* serogroups A, C, W and Y at approximately 1 year after completion of a 4-dose

Name of Sponsor:	Protocol number:	Generic name of study vaccine(s):
Novartis Pharma Services AG	V59_75	MenACWY-CRM (Menveo®) is a Meningococcal (Groups A, C, Y and W-135), Oligosaccharide Diphtheria CRM 197 Conjugate Vaccine.

infant vaccination series (2, 4, 6 and 12 months of age) of MenACWY vaccine as measured by hSBA GMTs and rSBA GMTs.

### Safety Objective(s)

To assess the safety and tolerability of MenACWY administered at 2-4-6 and 12 months of age.

### **Study Design:**

This is Phase IV, Open label, Multicenter study. Subject's parents and/or legal guardian will be provided information about the trial. If interested and if eligible, they will then be asked to provide signed informed consent. The initial study visit can occur immediately after signed informed consent has been obtained. Approximately 135 subjects will be enrolled to receive 4 doses of intramuscular MenACWY vaccine at 2, 4, 6 and 12 months of age.

A total of two blood samples (up to approx. 5 mL per draw) will be obtained at 13 and 24 months of age.

**Table 1:** Overview of the Study design

No Subjects	Visit 1	Visit 2	Visit 3	Visit 4	Visit 5	Visit 6
No Subjects	2-Months	4-Months	6-Months	12-Months	13- Months	24- Months
135	Menveo®	Menveo®	Menveo®	Menveo®	Blood draw	Blood draw

### **Table 2:** Safety Assessment

Medical history:	From birth
Any significant past (see details in Section 4.2 and 6.2 of the protocol)	

Doc Number: 68901057

Name of Sponsor:	Protocol number:	Generic name of study vaccine(s):				
Novartis Pharma Services AG	V59_75	MenACWY-CRM (Menveo®) is a Meningococcal (Groups A, C, Y and 135), Oligosaccharide Diphtheria CRM 197 Conjugate Vaccine.				
Vaccination history:			From birth			
Will be checked to det criteria.	termine subject's eligibi	llity				
Immediate reactions	;		For 30 minutes after each			
Subjects will be assess	sed for immediate reacti	ions	Men ACWY vaccination			
recommended, but axi temperature cannot be	Body Temperature: Body Temperature (tympanic is recommended, but axillary, rectal route is allowed if temperature cannot be taken by tympanic route) and antipyretic/analgesic use will be recorded.					
Solicited local advers	-	From Day 1 to Day 7 after each Men ACWY vaccination				
	Solicited systemic adverse events: Change in eating habits, sleepiness, irritability, vomiting, diarrhea, fever.					
Unsolicited Adverse unsolicited AEs and A withdrawal will be col visits	From Day 1 of the study to Visit 6 (24 months of age)					
Serious AEs (SAEs): resolution and/or the cremains unresolved at assessment will be ma Novartis medical mon continued follow up of	From Day 1 of the study to Visit 6 (24 months of age)					
Medications: Medica attended AE, AEs lead SAE, verbally during a	From Day 1 of the study to Visit 6 (24 months of age)					

Name of Sponsor:	Protocol number:	Generic name of study vaccine(s):
Novartis Pharma Services AG	V59_75	MenACWY-CRM (Menveo®) is a Meningococcal (Groups A, C, Y and W-135), Oligosaccharide Diphtheria CRM 197 Conjugate Vaccine.

**Number of Subjects planned:** Approximately 135 subjects will be enrolled in this study.

# **Study Population and Subject Characteristics:**

The list of inclusion and exclusion criteria is included in protocol section 4.0, Selection of Study Population.

# **Study Procedures:**

Visit 1 (Age 2 months) (Day 1). Informed consent must be obtained from the subject's parent(s) or legally acceptable representative(s) prior to the performance of any study related procedures. After receiving the 1st vaccination, subjects will be observed for at least 30 minutes for any immediate reactions. The subjects' parents/legal guardian will be instructed to complete a subject diary daily, reporting solicited local and systemic adverse events (AEs) occurring from Day 1 to Day 7after vaccination with MenACWY.

At Day 3 after vaccination a telephone call will be made to remind the subjects' parents/legal guardian to complete the subject diary.

Visit 2 (Age 4 Months) (60 days after Visit 1 +/- 7 days). The subject diary will be collected and reviewed with all subject's parents/legal guardian. After receiving the 2nd vaccination, subjects will be observed for at least 30 minutes for any immediate reactions. The subjects' parents/legal guardian will be instructed to complete a subject diary daily, reporting solicited local and systemic adverse events (AEs) occurring from Day 1 to Day 7 after vaccination with MenACWY.

At Day 3 after vaccination a telephone call will be made to remind the subjects' parents/legal guardian to complete the subject diary.

Visit 3 (Age 6 months) (60 days after Visit 2 +/- 7 days). The subject diary will be collected and reviewed with all subject's parents/legal guardian. After receiving the 3rd vaccination, subjects will be observed for at least 30 minutes for any immediate reactions. The subjects' parents/legal guardian will be instructed to complete a subject diary daily, reporting solicited local and systemic adverse events (AEs) occurring from

Doc Number: 68901057

Name of Sponsor:	Protocol number:	Generic name of study vaccine(s):
Novartis Pharma Services AG	V59_75	MenACWY-CRM (Menveo®) is a Meningococcal (Groups A, C, Y and W-135), Oligosaccharide Diphtheria CRM 197 Conjugate Vaccine.

Day 1 to Day 7 after vaccination with MenACWY.

At Day 3 after vaccination a telephone call will be made to remind the subjects' parents/legal guardian to complete the subject diary.

Visit 4 (Age 12 Months) (Inclusive + 14 days). The subject diary will be collected and reviewed with all subject's parents/legal guardian.

After receiving 4th vaccination, subjects will be observed for at least 30 minutes for any immediate reactions. The subjects' parents/legal guardian will be instructed to complete a subject diary daily, reporting solicited local and systemic adverse events (AEs) occurring from Day 1 to Day 7 after vaccination with MenACWY.

At Day 3 after vaccination a telephone call will be made to remind the subjects' parents/legal guardian to complete the subject diary.

Visit 5 (Age 13 Months) (30 days after Visit 4:-7, +14 days). The subject diary will be collected and reviewed with all subject's parents/legal guardian. A blood sample of approximately 5ml will be collected to evaluate the level of bactericidal antibodies.

Visit 6 will be appointed for when subject reaches 24 months of age (+/-60 days).

Visit 6 (24 months of age: +/- 60 days). A blood sample of approximately 5ml will be collected to evaluate the level of bactericidal antibodies. Any symptoms or medical events that are new or changed since previous visit, such as SAEs, medically attended AEs or AEs leading to premature withdraw, and medications used to treat them.

All blood draws should be delayed in case the subjects received oral or parenteral antibiotic treatment in the 7 days prior to the scheduled blood draw.

## **Study Vaccines:**

The study Novartis MenACWY vaccine is obtained by extemporaneous mixing just before injection of the lyophilized Men A component to be re-suspended with the liquid Men CWY component. After reconstitution the MenACWY vaccine will have the following composition per 0.5 mL of injectable solution:

Name of Sponsor:	Protocol number:	Generic name of study vaccine(s):
Novartis Pharma Services AG	V59_75	MenACWY-CRM (Menveo®) is a Meningococcal (Groups A, C, Y and W-135), Oligosaccharide Diphtheria CRM 197 Conjugate Vaccine.

Table 3: Composition of Novartis MenACWY Conjugate Vaccine

Name of Ingredients	Quantity per dose
CRM 197 -MenA conjugate	10 μg MenA, 12.5 – 33 μg CRM 197
CRM 197 -MenC conjugate	5 μg MenC, 6.5 - 12.5 μg CRM 197
CRM 197 -MenW conjugate	5 μg MenW, 3.3 – 10 μg CRM 197
CRM 197 -MenY conjugate	5 μg MenY, 3.3 – 10 μg CRM 197
Sodium chloride	4.5 mg
Sucrose	12.5 mg
Sodium phosphate buffer	10 mM
Potassium dihydrogen phosphate	5 mM
Water for injection	qS to 0.5 mL

# Primary Endpoint(s): Immunogenicity Endpoint(s).

No specific criteria are established to assess adequacy of the antibody persistence. All analyses will be run descriptively.

- Percentage of subjects with hSBA  $\geq$  8 at Visits 5 and 6
- hSBA GMTs at Visits 5 and 6
- Percentage of subjects with rSBA  $\geq$  8 at Visits 5 and 6
- Percentage of subjects with rSBA  $\geq$  128 at Visits 5 and 6

Name of Sponsor:	Protocol number:	Generic name of study vaccine(s):
Novartis Pharma Services AG	V59_75	MenACWY-CRM (Menveo®) is a Meningococcal (Groups A, C, Y and W-135), Oligosaccharide Diphtheria CRM 197 Conjugate Vaccine.

• rSBA GMTs at Visits 5 and 6

### **Safety Endpoint(s):**

Percentage of subjects with:

- Immediate reactions reported within 30 minutes after vaccination.
- Solicited local and systemic adverse events from Day 1 to Day 7 following each vaccination
- Medically-attended unsolicited AEs and AEs leading to premature withdraw from Day 1 to Visit 6 (at 24 months of age)
- SAEs from Day 1 to Visit 6 (at 24 months of age)

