#### **Statistical Analyses:**

There is no statistical hypothesis associated with the immunogenicity objective. All analyses will be run descriptively.

The primary objective is to evaluate the persistence of the antibody response against N. *meningitidis* serogroups A, C, W and Y at approximately 1 year after completion of a 4-dose infant vaccination. This persistence will be summarized as the percentage of subjects with a titer  $\geq 8$  (hSBA) or with a titer  $\geq 8$  and  $\geq 128$  (rSBA) along with associated two-sided 95% Clopper-Pearson confidence intervals.

The antibody titers will be summarized using GMTs with two-sided 95% confidence intervals constructed by exponentiation (base 10) of the means and confidence limits of the logarithmically transformed (base 10) antibody titer. Moreover the geometric mean ratios (GMR) between visit 6 (1 year after full vaccination) and visit 5 (1 month after full vaccination) will be provided along with the 2-sided 95% confidence intervals.

Approximately 135 subjects will be enrolled in this study providing approximately 100 evaluable subjects, assuming a 25% drop-out. The sample size is based on the number of subjects requested and agreed with South Korean Health Authorities for this persistence

Name of Sponsor:	Protocol number:	Generic name of study vaccine(s):
Novartis Pharma Services AG	V59_75	MenACWY-CRM (Menveo®) is a Meningococcal (Groups A, C, Y and W-135), Oligosaccharide Diphtheria CRM 197 Conjugate Vaccine.

study.

With 100 evaluable subjects, the 95% confidence limits of the observed percentages of subjects with hSBA titer  $\geq$ 8 or rSBA titer titer  $\geq$  8 or  $\geq$ 128 will be as presented in the following table.

Table 4: Calculated 95% Confidence Interval, Associated With Different Observed Percentages of Subjects

Observed percentage	95% confidence interval (Menveo® N=100)
50%	40%- 60%
60%	50%-70%
70%	61%-79%
80%	72%-88%
90%	84%-96%

Dependent on the point estimate, the length of the confidence interval will be 12% - 20%.

The analyses will be done on the Full Analysis Set (FAS population).

Additional details will be described in the statistical analysis plan.

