### 3.2 Study Period

Each subject should expect to participate in the study for 22 months, from the time of enrolment through the last study visit.

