## 5.5 Study Termination Visit

The study termination visit will occur on day 661. The termination visit may be a clinic visit or a telephone call. The date of termination is the date of the last contact (clinic visit or telephone call) in which the subject's health status was assessed or, in cases where the subject does not agree to any further safety follow-up, it is the date consent is withdrawn. This date should be recorded on the termination CRF page. For visit procedures to be performed for a subject whose planned study participation ends prematurely, please see section 5.5.1, Early Termination Visit.

Doc Number: 68901057

At the clinic visit or during the telephone call, the following procedures will be performed:

- Review of the safety information that includes review of Subject Diary, review of systems, interview of subject parent(s)/legal guardian(s) to collect any medically attended adverse events, AEs leading to withdrawal, SAEs
- Interview of subject parent(s)/legal guardian(s) to collect concomitant medications/ vaccinations associated with the AEs listed above, Symptom-directed physical assessment is to be performed as needed (including measurement of vital signs, body temperature and a check of general appearance)
- Collection of the last blood sample as specified in section 3.5 and section 4.3.
- The site will review with the subject parent(s)/legal guardian(s) the plan of when information relating to the subject's participation in the study may be available (e.g., study results, treatment assignments). It will also be discussed how information relating to the subject's participation in the study will be shared with the subject's healthcare provider, if the subject parent(s)/legal guardian(s) chooses to share this information

The site will complete the termination CRF page and this will mark the completion of the subject's participation in the study.

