# 8.5 Sample Size and Power Considerations of Primary and Secondary Objectives

Approximately 135 subjects will be enrolled in this study providing approximately 100 evaluable subjects, assuming a 25% drop-out. The sample size is based on the number of subjects requested and agreed with South Korean Health Authorities for this persistence study.

With 100 evaluable subjects, the 95% confidence limits of the observed percentages of subjects with hSBA titer  $\geq 8$  or rSBA titer titer  $\geq 8$  or  $\geq 128$  will be as presented in the following table.

Table 8.5-1: Calculated 95% Confidence Interval, Associated With Different Percentages of Observed Percentages of Subjects

Observed percentage	95% confidence interval (Menveo® N=100)
50%	40%- 60%
60%	50%-70%
70%	61%-79%
80%	72%-88%
90%	84%-96%

Dependent on the point estimate, the length of the confidence interval will be 12% - 20%.

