# 7.7 Overview of Analysis Sets by PD Code

**Table 7.7-1:** Unsolicited Safety Sets

PD code	PD Description	Study Objective/ Period	Safety Set, Unsolicited AEs, Period 1	Safety Set, Unsolicited AEs, Period 2	Safety Set, Unsolicited AEs, Period 3	Safety Set, Unsolicited AEs, Period 4	Safety Set, Unsolicited AEs, Overall
	Exclusion code		SSU10FL	SSU11FL	SSU12FL	SSU13FL	SSUFL
100	Study vaccine not administered AT ALL	All Study	EXC	EXC	EXC	EXC	EXC
115.1	Subject did not provide any post-vaccination unsolicited safety data in period 1	Visit 1/Day 1 to Visit 2/Day 61	EXC	None	None	None	None
115.2	Subject did not provide any post-vaccination unsolicited safety data in period 2	Visit 2/Day 61 to Visit 3/Day 121	None	EXC	None	None	None
115.3	Subject did not provide any post-vaccination unsolicited safety data in period 3	Visit 3/Day 121 to Visit 4/Day 301	None	None	EXC	None	None
115.4	Subject did not provide any post-vaccination unsolicited safety data in period 4	Visit 4/Day 301 to Visit 6/Day 661 or Study End	None	None	None	EXC	None

EXC = excluded from this analysis set; None=No exclusion;

.

Table 7.7-2: Exposed, Overall and Solicited Safety Sets

	- _							
PD code	PD Description	Study Objective/ Period	All Exposed Set	Overall Safety Set	Safety Set, Solicited AEs, Period T6H*-D7	Safety Set, Solicited AEs, Period T6H*-D3	Safety Set, Solicited AEs, Period D4-D7	Safety Set, Solicited AEs, Period T30m*
	Exclusion code		EXPFL	SAFFL	SSS10FL	SSS11FL	SSS12FL	
100	Study vaccine not administered AT ALL	All Study	EXC	EXC	EXC	EXC	EXC	EXC
116.1	Subject did not provide any post-vaccination solicited safety data after vaccination 1	Day 1 through Day 7 after Vaccination 1	None	None	EXC	EXC	EXC	None
116.2	Subject did not provide any post-vaccination solicited safety data after vaccination 2	Day 1 through Day 7 after Vaccination 2	None	None	EXC	EXC	EXC	None
116.3	Subject did not provide any post-vaccination solicited safety data after vaccination 3	Day 1 through Day 7 after Vaccination 3	None	None	EXC	EXC	EXC	None
116.4	Subject did not provide any post-vaccination solicited safety data after vaccination 4	Day 1 through Day 7 after Vaccination 4	None	None	EXC	EXC	EXC	None

\* T30m and T6H=Day 1 time points of 30 min and 6 hrs respectively following vaccination; EXC = excluded from this analysis set. None=No exclusion;

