# 8.2 Handling of Dropouts, Missing Data

First-line analyses will be without missing values.

To minimize the effect of dropouts and missing data the study period will be divided into time intervals for statistical analysis of safety.

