#### 13.3 Unsolicited Adverse Events

The first-line analysis will use unsolicited adverse event data from all reporting sources combined. A second-line analysis will encompass the analysis of unsolicited adverse events by source (e.g. diary cards, medical records, study specific worksheet).

All the unsolicited adverse events occurring during the study, judged either as probably related, possibly related, or not related to vaccination by the investigator, will be recorded. The original verbatim terms used by investigators to identify adverse events in the CRFs will be mapped to preferred terms using the MedDRA dictionary. The unsolicited adverse events will then be grouped by MedDRA preferred terms into frequency tables according to system organ class. Adverse events judged by the investigator as at least possibly related to study vaccine will be summarized, according to system organ class and preferred term within system organ class. When an unsolicited adverse event occurs more than once for a subject, the maximal severity and strongest relationship to the vaccine group will be counted.

Only vaccine-emergent adverse events (see section 8.7 for definition) will be analyzed, i.e., excluding those after a subject has given informed consent but before vaccination. The selection of unsolicited adverse events and the assignment to time intervals will be done by day of onset and not by days ongoing/persisting.

The summaries will be presented by onset and will include frequency distributions of the different adverse events:

- Vaccination period 1: Onset between visit 1/day 1 and visit 2/day 61.
- Vaccination period 2: Onset between visit 2/day 61 and visit 3/day 121.
- Vaccination period 3: Onset between visit 3/day 121 and visit 4/day 301.
- Vaccination period 4: Onset between visit 4/day 301 and visit 6/day 661or study termination.
- Overall

The analysis of unsolicited adverse events comprises the following categories:

- Medically attended unsolicited adverse event.
- Possibly or probably related medically attended unsolicited adverse events.
- Unsolicited adverse events leading to death.
- Serious adverse events.
- Possibly or probably related serious adverse event.
- Unsolicited adverse events leading to premature withdrawal from study.
- Unsolicited adverse events leading to dose reduction, interruption or delay in study vaccination.
- Unsolicited adverse events leading to hospitalization.

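### The Overall Day 1 to Visit 6 safety percentages, and to a lesser extent those for Period 4, make no correction for incomplete follow-up and would understate risk if children are lost to safety follow-up.

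*Protocol*

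**What the plan says.** Safety is a primary objective (Protocol 2.1; SAP 2.1). The synopsis defines the long-term safety endpoints as percentages of subjects, among them "Medically-attended unsolicited AEs and AEs leading to premature withdraw from Day 1 to Visit 6 (at 24 months of age"), with SAEs over the same window. Protocol 8.1.1.1 repeats this. Follow-up is long: "Each subject should expect to participate in the study for 22 months, from the time of enrolment through the last study visit".

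SAP version 2 does address drop-out. Section 8.2 states: "To minimize the effect of dropouts and missing data the study period will be divided into time intervals for statistical analysis of safety". Sections 7.5 and 13.3 then set up four vaccination periods plus Overall. The last period is defined as follows: "Vaccination period 4: Onset between visit 4/day 301 and visit 6/day 661or study termination".

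Table 7.7-1 gives the exclusion codes. Codes 115.1 to 115.4 each remove a child from the one period in which that child gave no data; 115.4, for example, reads "Subject did not provide any post-vaccination unsolicited safety data in period 4". In the Overall column all four codes show no exclusion, and only code 100 (never vaccinated) excludes.

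SAP 8.2.1 rules out imputation of missing safety values. SAP 9.1 summarises time under observation, but no analysis uses it as a denominator, and SAP 13.3 plans no incidence rate or time-to-event estimate.

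**The concern.** A crude percentage over Day 1 to Visit 6 gives a child seen for two months the same weight as a child seen for 22. Neither document calls the early leaver event-free, but a simple proportion without imputation has that effect for the unobserved time. The period split does not reach the Overall row, which is the window the protocol endpoint names.

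It helps only partly in Period 4, which runs from Day 301 to Day 661 and accepts follow-up that ends at study termination. No visit falls between Day 331 and Day 661. There are no safety follow-up calls (Protocol 5.3.2), and medically attended AEs are captured by interview at clinic visits (Protocol 3.1). A child last interviewed at Visit 5 has given Period 4 data, so code 115.4 does not apply, yet the interview covered only about 30 of the 360 days.

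The SAP guards against this kind of bias elsewhere. For solicited events (SAP 13.2) it takes subjects without plausible data out of the denominator so that percentages are not pulled towards zero. The 22-month percentages have no equivalent safeguard. With one arm and no comparator, nothing cancels: the absolute percentage is the result.

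**Working it through.** **The plan's own figure.** Protocol 8.5 states: "Approximately 135 subjects will be enrolled in this study providing approximately 100 evaluable subjects, assuming a 25% drop-out". Check: 100 / 0.75 = 133.3, rounded up to 134, against 135 planned; 135 × 0.75 = 101.25, against about 100. The figure reproduces, and it is a serology figure: the precision table that follows it is for hSBA and rSBA percentages. The documents give no expected AE percentage and no rate of loss to safety follow-up, so there is no safety figure to reproduce.

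**Inputs.** Window: Day 1 to Day 661, 660 days. Period 4: Day 301 to Day 661, 360 days.

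**Assumptions.** True risk p of 5% or 50%; constant hazard; loss d of 5%, 10% or 25%; exit uniform over the window.

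**Formula.** Hazard λ = −ln(1 − p)/660. Reported percentage = (1 − d)·p + d·m, where m is the mean risk accrued before exit. For uniform exit, m = 1 − p/(−ln(1 − p)).

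- p = 50%: m = 1 − 0.5/0.6931 = 0.2787, so reported = 0.5 − 0.2213·d.
- p = 5%: m = 1 − 0.05/0.05129 = 0.0252, so reported = 0.05 − 0.0248·d.

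| True risk | 5% loss | 10% loss | 25% loss |
|---|---|---|---|
| 50% | 48.9% | 47.8% | 44.5% |
| 5% | 4.9% | 4.75% | 4.4% |

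In children out of 135, a true 50% is 67.5. At 10% loss it is reported as about 64.5 (135 × 0.478), and at 25% as about 60 (135 × 0.445). A true 5% is 6.75, reported as about 5.9 at 25% loss.

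**Sensitivity to timing, at 25% loss.**

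- All exits uniform between Visits 5 and 6: 50% is reported as 47.6%, 5% as 4.7%.
- All exits uniform before Day 121: 39.0% and 3.9%. This overstates the effect, because a child with only 30-minute data is excluded (SAP 7.5). If those leaving before Day 60 are removed, 50% becomes (0.75 × 0.5 + 0.125 × 0.090)/0.875 = 44.1%, and 5% becomes 4.4%.
- Safety follow-up completed despite withdrawal: no bias.

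**Period 4.** With 25% uniform loss over 660 days, 0.25 × 300/660 = 11.4% leave before Day 301. Of the remaining 88.6%, 0.25 × 360/660 = 13.6% of the original number leave during the period, which is 15.4% of those entering. A true Period 4 risk of 50% is reported as 0.5 − 0.154 × 0.2213 = 46.6%. In relative terms that is about 7% too low, against 11% for the Overall row. If instead 15% were all last observed right after Visit 5, 50% would become 0.85 × 0.5 + 0.15 × (1 − 0.5^(30/360)) = 43.3%.

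**The case against.** The strongest reply is that the 25% is not a safety-loss rate. It takes 135 enrolled children to about 100 evaluable for serology. A child without a usable Visit 6 sample may still be fully observed for safety. Withdrawn children are asked to stay in safety follow-up (Protocol 3.8), and withdrawal of consent may leave safety participation in place. Lost families get repeated contact attempts, the termination visit may be by telephone (Protocol 5.5), and the early termination visit collects SAEs and medically attended AEs (Protocol 5.5.1). Parents are also told to call the site about hospital or doctor visits.

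This stands. A reader might infer that the plan's own drop-out assumption biases the safety results by a tenth or more. The documents do not support that. They do not exclude loss either: continued follow-up is a request, and both complete withdrawal and loss to follow-up are provided for.

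A second reply is that early leavers are not all kept. Children with only 30-minute data are excluded, and later periods drop those without data. This also stands, and it weakens the scenario in which everyone leaves early. It does not touch the Overall row for a child seen at Visit 2 and then lost, or the tail of Period 4.

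Third, the set definition (exposed subjects with unsolicited AE data) could be read as only children who reported an event, which would push percentages up. That is a separate ambiguity. The 115 codes speak of not providing any data, which fits the ordinary reading better.

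Fourth, materiality. The study is descriptive, with no safety success criterion. At a true 5%, even 25% loss moves the count by less than one child, while the exact 95% CI for 7/135 is about 2.1% to 10.4%. For rare events the bias is small beside the sampling error.

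**Conclusion.** The concern holds conditionally. The Overall Day 1 to Visit 6 percentages for SAEs, medically attended AEs and AEs leading to withdrawal, and to a lesser extent the Period 4 percentages, are not corrected for incomplete follow-up. If children are lost to safety follow-up, these percentages understate the 22-month risk.

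On a constant hazard and uniform exit, the relative understatement is about 2% to 5% for loss of 5% to 10%, and about 11% to 12% at the 25% upper planning case, for true risks of 50% and 5%. It is nil if withdrawn children complete safety follow-up. The true risks, the hazard shape, the loss rate and the exit timing are all assumptions.

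A reader might go further and say that every early leaver is counted as event-free throughout. That is not so: events before exit count, and children with only 30-minute data leave the set. No hypothesis test or between-arm comparison is affected. This is a cheap improvement to a primary safety summary, most useful for common events such as medically attended AEs.

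**What to change.** In SAP 13.3, keep the crude percentages as the protocol-defined endpoint. Beside them, for SAEs and for medically attended AEs, Overall and in Period 4, add a Kaplan-Meier cumulative risk of first event with a 95% CI. Two rules need to be written down.

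- **Censoring date.** Use the last contact at which health status was assessed, in line with Protocol 5.5: "The date of termination is the date of the last contact (clinic visit or telephone call) in which the subject's health status was assessed". The lost-to-follow-up text in Protocol 3.8 uses the last successful contact of any kind, which could be a diary reminder call. The termination date on the CRF should therefore not be used unchecked.
- **Partial onset dates.** SAP 8.7 covers only whether an event is emergent, and SAP 8.2.1 rules out imputation. State how an event with an incomplete date is placed in time.

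Cost: SAP wording and a few more tables, with no new data collection. The reported risks will be slightly higher than the crude percentages, and the estimate assumes that censoring is unrelated to events, which should be stated next to the tables.
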